3.4.7 Limitations

Based on restrictions in Canada, diagnosis can only be inferred. Therefore on-label and off-label use is an estimation based on the applied rules. The off-label use is likely over-estimated as the rules to include a patient in on-label and stringent and all other patients are considered off-label.

Counter indications such as diabetic ketoacidosis, diabetic coma/precoma and end-stage renal failure cannot be inferred from the data source. Therefore, these patients will not be identified in the study.

There is differing amount of information for each patient due to the fixed time frame of the analysis. Since each patient will have a different index date the amount of data will differ for those patients who initiate Byetta at the start of the analysis period compared to patients who initiate Byetta at the end of the analysis

period. This is ensures we have as much data available as possible for each patient so they can be classified appropriately

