3.1 Rationale

Exenatide is an injectable glucagon-like peptide 1 (GLP-1) receptor agonist approved as an adjunct to diet and exercise to improve glycemic control in adults with type 2 diabetes mellitus (T2DM) by the United States and Europe. Byetta (exenatide twice daily) is administered as a subcutaneous injection within 1 hour before the two main meals of the day, approximately 6 hours or more apart. Treatment is typically initiated at 5 mcg per dose, twice daily, and may be increased to 10 mcg twice daily based on the patient’s clinical response.

During Health Canada’s review of the marketing authorisation application of exenatide, Lilly provided a commitment to monitor the off-label use and compliance to the Summary of Product Characteristics (SPC) of exenatide prescriptions through a post-launch utilization study. Specifically, Health Canada requested that:

The RMP should be revised to include a post-marketing study conducted on exenatide use and adherence to labeling recommendations in Canada, similar to the drug utilization study requested by the EU Regulatory authority that is currently ongoing in various EU countries. Since preliminary information has already indicated off label use of exenatide with either TZD or insulin in the EU, the need for further study and/or additional risk management actions with these products should be specifically addressed.

Table 1: Canadian Byetta Indication

Byetta Monograph
Indication and Clinical Use:
BYETTA is indicated in combination with metformin and/or sulfonylurea to improve glycemic control in patients with type 2 diabetes mellitus, when maximally tolerated doses of these oral therapies in addition to diet and exercise do not provide adequate glycemic control.
BYETTA is indicated in combination with insulin glargine (with or without metformin) to improve glycemic control in patients with type 2 diabetes mellitus when insulin glargine (with or without metformin) in addition to diet and exercise, does not provide adequate glycemic control
Contraindication:
BYETTA should not be used in the pediatric patient population.

BYETTA should not be used in patients with end-stage renal disease or severe renal impairment (creatinine clearance <30 mL/min), including patients receiving dialysis

BYETTA is contraindicated in patients with diabetic ketoacidosis, diabetic coma/precoma or type 1 diabetes mellitus.

Source: Byetta Drug Product Monograph, Canadian Pharmacists Association, online version, April 2011.

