3.4.4 Study Outcomes and Definitions

[figure not shown]
The primary outcome of interest is the off label use of Byetta in Canada.

A patient's therapy type will be inferred by identifying if a patient switches between, or adds on to therapies, as shown in figure 3.

Mono Therapy is defined as a patient receiving a specific therapy (Therapy 1) prior to a different therapy (Therapy 2) where Therapy 1 is not detected after Therapy 2 initiation. Mono therapy for this study, refers to a patient received a prescription for only one product at a given time.

Concomitant Therapy is defined as a patient receiving a specific therapy (Therapy 1) prior to a different therapy (Therapy 2) where Therapy 1 is detected after Therapy 2 initiation.

Figure 3: Distinguishing between add-on and switch therapies

Patients will be selected for the study if they receive a Byetta script anytime during the analysis period and if they met the inclusion criteria. To identify on-label vs. off-label use, patient history will then be used to classify patients as "inferred on-label" if they also received Metformin and/or SU or Lantus during the study (Business rules 1 and 2 in Table 5).

All other patients that do not meet the criteria for use of Byetta with metformin and/or SU or Lantus will be classified as “inferred off-label”. The group of patients classified as “inferred off-label” will then be further classified to gain a better understanding of the trends in “inferred off-label” use of Byetta (Business rules 3-10 in Table 5).

The Business rules described in Table 5 are prioritized to ensure the appropriate classification of each patient. Therefore patients will be classified based on the highest rank business rule. For example, if a patient receives scripts for both Metformin and other insulin during the analysis period, they will be classified as “inferred on-label” as they have a script for metformin and therefore are classified by business rules 1 and 2

Note: The patient classification categories (‘Inferred Adherence Label’) can be modified in the initial phase of the project.

Table 5: Business rules applied to classify patients as “on-label” vs. “off-label”

(The business rules have been structured to align with the Canada monograph for Byetta indication and clinical use (see Table 1) and will be finalized upon study initiation).

Rank	Business Rules	Cohort Description	Inferred Adherence Label

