1	Concomitant use of* Byetta with metformin (met) and/or sulfonylurea (SU), OR Concomitant use of Byetta with Lantus	Met and/or SU or Lantus is prescribed with Byetta	Inferred On-label
2	Evidence of** Byetta and metformin and/or sulfonylurea OR Evidence of Byetta and Lantus	Met and/or SU or Lantus is not prescribed with Byetta, but both appear in the analysis period	Inferred On-label
3	Evidence of Byetta and Levemir	Levemir is prescribed in the analysis period	Off-Label Insulin Use
4	Evidence of Byetta and Human Basal Insulin	Human basal insulin is prescribed in the analysis period	
5	Evidence of Byetta and thiazolidinedione (TZD)	TZD is prescribed in the analysis period	Off-Label OAD Use

6	Byetta Alone	No other products prescribed in the analysis period	Inferred Off-label
7	Evidence of Byetta and all other insulin	Other insulin is prescribed in the analysis period	
8	Evidence of Byetta and all other OADs	Other OADs are prescribed in the analysis period	
9	Pediatric Patients	Patient is under the age of 18 (<18)	
10	All other combinations	All other combinations	

Note: Evidence of Diabetic ketoacidosis, diabetic coma/precoma and end stage renal disease cannot be inferred from the dataset; therefore we will not be able to identify these patients as a separate group

* "Concomitant use of..." refers to continued use of Byetta and other product

** "Evidence of..." refers to anytime within the study period including look-back or look forward periods

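### The protocol calls off-label use over-estimated because its on-label rules are stringent, but those rules are permissive and the net direction of bias is not established

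*Protocol*

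**What the plan says.** Section 3.4.7 states both a direction of bias and a cause: "The off-label use is likely over-estimated as the rules to include a patient in on-label and stringent" (the last words evidently mean that the rules are stringent). It adds that everyone else counts as off-label.

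The rules themselves are in section 3.4.4 and Table 5:

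- Rank 1 is on-label: Byetta used concomitantly with metformin and/or SU, or with Lantus.
- Rank 2 is also on-label. Its cohort is described as "Met and/or SU or Lantus is not prescribed with Byetta, but both appear in the analysis period", and the footnote says that evidence of a product "refers to anytime within the study period including look-back or look forward periods".
- On ranking: "Therefore patients will be classified based on the highest rank business rule". The protocol's own example is that "if a patient receives scripts for both Metformin and other insulin during the analysis period, they will be classified as" inferred on-label.
- Levemir is rank 3, human basal insulin rank 4, TZD rank 5 and other insulin rank 7.
- On the remainder: "All other patients that do not meet the criteria for use of Byetta with metformin and/or SU or Lantus will be classified as" inferred off-label.

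Table 1 in section 3.1 gives the label. The oral-therapy indication applies "when maximally tolerated doses of these oral therapies in addition to diet and exercise do not provide adequate glycemic control", and the insulin indication is for glargine, with or without metformin, when control is inadequate.

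**The concern.** A limitation that names a direction of bias tells the reader how to use the estimate. If off-label use is said to be over-estimated, the reported percentage will be read as a cautious upper figure. That reading rests on the on-label rules being hard to meet, and the rules in section 3.4.4 look easy to meet.

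Off-label use is the primary outcome. Use with a TZD or insulin is the secondary objective and the use that the regulator singled out in section 3.1. Under Table 5, much of that co-use can be absorbed into the on-label group, because metformin, SU or Lantus evidence takes precedence over it. A regulator could then be reassured by a direction of bias that the plan has not shown.

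**Working it through.** The protocol gives no expected off-label share, so there is no figure to reproduce. The check has three steps.

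**1. Rules against label**

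| Label element (Table 1) | Rule (Table 5) | Effect on measured off-label use |
|---|---|---|
| Used in combination with metformin/SU or glargine | Rank 2 needs no use alongside Byetta | Down |
| Glargine is the only insulin named; TZD is not named | Ranks 1–2 outrank Levemir, human basal, TZD and other insulin | Down |
| Maximally tolerated oral doses; inadequate control | Not tested by any rule | Down |

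The rank 2 cohort text speaks of the analysis period, while the footnote extends it to look-back and follow-up. Even on the narrower window, rank 2 asks for no overlap with Byetta.

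**2. Can the rules err in the stated direction?** Take eight co-medication classes (metformin, SU, Lantus, Levemir, human basal, other insulin, TZD, other OAD). Set each to absent, seen but not with Byetta, or concomitant. That gives 3^8 = 6,561 profiles.

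- Off-label by the rules: no metformin, SU or Lantus at all, so 3^5 = 243.
- Most lenient label reading (any concomitant metformin, SU or Lantus; other drugs ignored): on-label by label = 6,561 − 2^3 × 3^5 = 4,617. Off-label by label but on-label by rule = 1,944 − 243 = 1,701.
- Strict reading (only metformin and/or SU, or only Lantus with or without metformin, used with Byetta): on-label by label = 128 + 128 + 64 + 128 + 64 = 512. Off-label by label but on-label by rule = 6,561 − 512 − 243 = 5,806.
- Strict reading that also allows Lantus with SU: on-label by label = 512 + 64 + 32 = 608. Off-label by label but on-label by rule = 5,710.
- On-label by label but off-label by rule: 0 in every reading.

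These are logical profiles, not patient frequencies. They show that, with complete records and separate drug classes, the rules move patients only from off-label to on-label.

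**3. What could reverse this?** Let p be the true off-label share, m the share of those patients with a qualifying script, and u the share of true on-label patients whose qualifying fills are not seen. Then

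measured off-label = p(1 − m) + (1 − p)u,

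and the biases cancel at u = pm/(1 − p). All values below are assumptions.

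| p | m | u = 0 | u = 0.05 | u = 0.10 | u = 0.25 | Break-even u |
|---|---|---|---|---|---|---|
| 0.30 | 0.5 | 15.0% | 18.5% | 22.0% | 32.5% | 0.15/0.70 = 0.214 |
| 0.10 | 0.5 | 5.0% | 9.5% | 14.0% | 27.5% | 0.05/0.90 = 0.056 |

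Table 2 puts national coverage at 74.6% of prescription volume (53.1% in Newfoundland/PEI). That figure does not convert directly into u. Patients enter only if their Byetta fills were captured, and several Table 3 exclusions aim to remove patients who use more than one pharmacy.

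**The case against.** The strongest reply is that real upward forces exist. Any patient without an observed qualifying fill defaults to off-label, so every missed fill of metformin, SU or Lantus counts that way. Section 3.4.7 itself says that the amount of data differs by index date, and a short record offers less chance to show qualifying evidence. There may also be a coding route: if any product that Table 4 files under TZD or DPP4 is a fixed combination containing metformin or SU (the protocol does not give compositions), a patient whose only metformin or SU comes that way could be placed off-label even with complete data. On the lenient reading, that would break the zero in step 2. All this stands, and it rules out asserting the opposite net direction. It does not rescue the sentence, because none of it is stringency of the on-label rules.

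Table 7 has a TZD row within the on-label column, so that co-use is not hidden. This also stands. As shown, however, Table 7 has a single insulin row, and neither table separates rank 2 from rank 1.

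The rules are provisional, and section 3.4.7 already calls both shares estimates and says that some contraindications cannot be seen. That is fair disclosure of uncertainty. The direction claim is nevertheless attached to the rules as written, and a contraindicated patient with a metformin script would count as on-label, which again runs against the stated direction.

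**Conclusion.** The reason given in section 3.4.7 is wrong as written. The ranked rules are permissive and, taken alone, push measured off-label use down. Incomplete capture, unequal record length and the default to off-label can push it up. The documents do not settle which prevails, so the result must not be presented as an over-estimate.

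A reader might infer that the reported share is therefore close to a lower bound. The documents do not support that either: on the assumed values above, missed fills in 5.6% of true on-label patients are enough to cancel the downward bias when the true share is 10%, against 21.4% when it is 30%.

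A reader might also point to patients under 18, whose rank 9 sits below the on-label ranks. That does not bear on Table 6, which covers adults; section 3.4.6 has pediatric off-label use described separately.

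The size of the rule effect depends on how Table 1 is read. On the lenient reading only the missing overlap in rank 2 matters; on the strict reading TZD and non-glargine insulin co-use matters as well. Table 5 itself places TZD and non-glargine insulin under off-label headings when metformin, SU and Lantus are absent.

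**What to change.** 1. Replace the sentence in section 3.4.7. State that the ranked rules tend to under-estimate off-label use (any-time evidence, precedence over TZD and other insulin, untested dose and control conditions), that incomplete capture works the other way, and that the net direction is unknown. If the Table 5 rules change when they are finalized, revisit this statement.
2. Beside Table 6, for adults, report how many inferred on-label patients qualify by rank 2 only, and how many used a TZD or a non-glargine insulin with Byetta. Count the latter on use with Byetta. Any-time evidence would repeat the looseness of rank 2 and would count a TZD stopped before Byetta.
3. Split the insulin row of Table 7 into glargine and non-glargine.
4. Show the off-label share with the patients in item 2 reclassified, as a sensitivity analysis beside the main figure.
5. Reconcile the rank 2 cohort description with the footnote on the time window.

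No under-18 count belongs beside Table 6. The cost is one reworded limitation and a few counts from data already extracted. The sensitivity figure can only be equal to or higher than the main one, so the headline may look less favourable.

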3.4.8 Adverse Events

Given the retrospective nature of this study (ie use of existing data), no AE data will be collected or reported from this study.

3.5 Dissemination Plan

This study will be used for regulatory purposes and dissemination.

The results may be presented at one or more scientific conferences. In addition, the results may be published in a relevant journal. However, IMS Brogan must be sourced as the supplier of the data and must provide written consent prior to publication or presentation.

4 References

N/A
